3.1. Stratification and Randomization

1. Hurley Stage (Stage II vs. III)
 - a. Stage II disease: one or more widely separated recurrent abscesses with tract formation and scars, or
 - b. Stage III disease: multiple interconnected tracts and abscesses across an entire area, with diffuse or near diffuse involvement.
2. Concomitant antibiotic therapy (Yes vs. No)

- a. Concomitantly treated with doxycycline or minocycline as the only allowed antibiotic treatment for HS, or
 - b. No concomitant antibiotic therapy.
3. Anti-TNF- α treatment (Treatment naïve vs. Previous treatment):
- a. Did not previously receive anti-TNF- α drug such as adalimumab or infliximab (anti-TNF- α drug naïve), or
 - b. Previously (but no longer) received an anti-TNF- α drug and
 - completed anti-TNF- α treatment but may have relapsed, or
 - was intolerant to anti-TNF- α treatment, or
 - previously failed to respond or inadequately responded to anti-TNF- α treatment.

Not more than 20% of subjects will be in stratum 2a as described above.

Eligible subjects will be randomized with equal chance (i.e., 1:1:1) to one of the three treatment groups within each stratum based on a non-dynamic, list-based blocked randomization scheme.

- 1) Placebo twice daily
- 2) Avacopan 10 mg twice daily
- 3) Avacopan 30 mg twice daily

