4.2. Exclusion Criteria

Subjects will be excluded from study participation if any of the following criteria are met:

1. Pregnant or breast-feeding;
2. Any other skin disease that may interfere with the assessment of HS, such as a viral or fungal skin infection;
3. Rapidly progressive, expanding HS within 30 days prior to Screening;
4. More than 20 draining fistulae at Screening;
5. Any anti-TNF- α treatment for HS or for other conditions prior to Day 1 visit will be prohibited. Exception: subjects who were previously treated with an anti-TNF- α drug and discontinued treatment >12 weeks prior to Day 1 visit are allowed for enrollment;
6. Systemic antibiotics are generally excluded. Exception: subjects on systemic antibiotic treatment with doxycycline or minocycline who have been on a stable dose for at least 28 days prior to Day 1. After a pre-specified percentage of subjects on these permissible antibiotic treatments have been enrolled, no further enrollment of such subjects will be allowed;
7. Topical antibiotics use within 14 days prior to Day 1;
8. Have started a topical prescription medicine for HS within 14 days prior to Screening or is anticipated to start during the Screening period. Topical prescription medicine for HS other than topical antibiotics that was started >14 days prior to Screening is allowed;
9. With the exception of permissible antibiotic treatment regimens, have received a systemic medicine for HS or with a potential therapeutic impact on HS, including systemic antibiotic therapy, biologics and other systemic therapies such as methotrexate, cyclosporine, retinoids,

and fumaric acid esters, etc., within a minimum of 30 days or 5 half-lives (whichever is longer) after taking the last dose;

10. Have received within 14 days prior to the Day 1 visit, or is expected to require during the study, oral or transdermal opioid analgesics (except for tramadol) for any reason; non-opioid analgesics are allowed if the subject is on a stable dose for at least 14 days prior to the Day 1 visit (“as needed” dosing is not considered to be a stable dose);
11. Currently taking a strong inducer of the cytochrome P450 3A4 (CYP3A4) enzyme, such as carbamazepine, phenobarbital, phenytoin, rifampin, or St. John's wort;

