5.7. Concomitant Therapy and Restrictions

No new treatment for HS (other than the study drug) may be introduced during the study period with the exceptions as outlined below.

All concomitant medications taken during the course of the study must be recorded meticulously on the concomitant medication pages in the EDC.

Anti- TNF- α Therapy, Systemic or Other Treatments with Potential Impact on HS:

Concomitant anti-TNF- α treatment during the trial is prohibited. Subjects who were previously treated with any anti-TNF- α drug and discontinued treatment >12 weeks prior to Day 1 visit would be allowed for enrollment.

Anti-TNF- α agents comprise five different FDA-approved drugs: adalimumab (Humira[®]), infliximab (Remicade[®]), entanercept (Enbrel[®]), golimumab (Simponi[®]), and certolizumab (Cimzia[®]). Of these anti-TNF- α agents, adalimumab, golimumab, and certolizumab share the longest mean terminal half-lives of 14 days as specified in their respective prescribing information labels. Subjects entering the trial need to be anti-TNF- α treatment-naïve or must have discontinued anti-TNF- α treatment for at least 12 weeks (which provides a washout period of over 5 times the half-life of any anti-TNF- α agent).

With the exception of permissible antibiotic treatment regimens, systemic or other treatments with a potential therapeutic impact on HS, including systemic antibiotic therapy, biologics and other systemic therapies such as methotrexate, cyclosporine, retinoids, and fumaric acid esters, etc., are prohibited.

Antibiotic Therapy: Concomitant use of oral antibiotic therapy for treatment of HS is generally not allowed. Systemic antibiotics (doxycycline or minocycline only) for the treatment of HS are permissible only for those subjects whose randomization was appropriately stratified for antibiotic use (see [Section 3.1 Stratification and Randomization](#)). During the study, the dose(s) of these drugs for the treatment of HS may not be increased. A systemic antibiotic must not be started for the treatment of HS during the course of the trial (treatment for a condition other than HS is allowed). However, the Investigators will be allowed to reduce the dose(s) or discontinue these ongoing antibiotic treatments during the study. Any dose changes in these treatments during the study must be recorded in the EDC system.

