The study is a randomized, double-blind, placebo-controlled, three-group Phase 2 trial in approximately 390 subjects with moderate to severe hidradenitis suppurativa (Hurley Stage II or III). Subjects will be randomized 1:1:1 to a treatment of 10 mg avacopan twice daily, 30 mg avacopan twice daily or placebo for 12 weeks. Other systemic treatments for HS including anti-TNF-α treatments are prohibited. Stable antibiotic therapy with doxycycline or minocycline is allowed as specified in the protocol. Subjects treated with 10 mg or 30 mg twice daily during the blinded, placebo-controlled 12-week treatment period (Period 1) will be followed by an additional 24-week, active treatment period (Period 2) during which they will continue to receive the same dose regimen, either 10 mg or 30 mg avacopan twice daily. Subjects on placebo who complete Period 1 will be re-randomized 1:1 to receive 10 mg or 30 mg avacopan twice daily in Period 2. During Period 2 the treatment assignment to 10 mg or 30 mg twice daily will not be disclosed to the subject, study site personnel or the Sponsor. Thereafter, all subjects will be followed for 8 weeks without study drug before they exit the study.

To obtain balance across treatment groups, a stratified randomization scheme will be implemented. The stratification factors and strata within each factor are listed below.

- Hurley Stage (Stage II vs. III):
 - Stage II disease: one or more widely separated recurrent abscesses with tract formation and scars, or
 - Stage III disease: multiple interconnected tracts and abscesses across an entire area, with diffuse or near diffuse involvement.
- Concomitant antibiotic therapy (Yes vs. No)
 - Concomitantly treated with doxycycline or minocycline as the only allowed antibiotic treatment for HS, or
 - No concomitant antibiotic therapy.
- Anti-TNF-α treatment (Treatment naïve vs. Previous treatment):
 - a. Did not previously receive anti-TNF-α drug such as adalimumab or infliximab (anti-TNF-α drug naïve), or
 - b. Previously (but no longer) received an anti-TNF-α drug and
 - completed anti-TNF-α treatment but may have relapsed, or
 - was intolerant to anti-TNF-α treatment, or
 - previously failed to respond or inadequately responded to anti-TNFα treatment.

Not more than 20% of subjects will be in stratum 2a.

For each subject, the study will consist of 4 periods:

- Screening Period (≤ 4 weeks)
- Double-Blind Treatment Period (12 weeks)
- Active Treatment Period (24 weeks)

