For secondary efficacy endpoint testing, the avacopan 30 mg vs. placebo or the avacopan 10 mg vs. placebo will be tested separately with the $\alpha = 0.05$ level, provided that the corresponding primary endpoint testing of the same dose level is significant. As the two drug doses are two independent families, and the outcome of the study is to select one dose, not 2 doses. A fixed hierarchical testing sequence will be employed, as following:

H₂: Change from Baseline in total AN count at Week 12

H₃: NRS30 at Week 12

H₄: % subjects with baseline Hurley Stage II who achieved AN count of 0, 1, or 2 at Week 12

H₅: Reduction of IHS4 at Week 12

H₆: Change from Baseline in inflammatory nodule count at Week 12

H₇: Change from Baseline in abscess count at Week 12

H₈: Change from Baseline in draining fistula count at Week 12

H₉: Change from Baseline in Modified Sartorius score at Week 12

Comparisons involving other efficacy endpoints and time points are considered supportive or exploratory and will be made at α =0.050 level (two-sided). No multiplicity adjustment will be made for these comparisons.

J. Analysis Populations

Analysis populations will be defined for use with various analyses.

Intent-to-Treat Population

The Intent-to-Treat (ITT) Population will include all subjects who are randomized and have received at least one dose of study drug, and who are not from study Site 138. Subjects from Site 138 will be excluded from the ITT Population due to potential misconduct and non-compliance at site 138.

The ITT populations are defined for the two treatment periods as the following:

- The ITT1 Population in Period 1 is defined as all subjects who are randomized at baseline and have received at least one dose of study drug during Period 1.
- The ITT2 Population in Period 2 is defined as all subjects who have received at least one dose of study drug during Period 2.

Per Protocol Population

The per protocol (PP) population for period 1 will consist of ITT1 and do not have protocol deviations that could significantly affect the interpretation of the results for the primary endpoints. Subjects' inclusion/exclusion from the PP population will be determined and documented prior to the database lock and unblinding.

Per-Protocol Population in Period 1 (PP1) will include subjects in ITT1 who meet all the following criteria:

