- Receive at least 70% of the planned study drug in Period 1 for subjects who complete Period 1 or receive at least one dose of study drug and discontinue Period 1
- Provide at least one post Baseline assessment on lesion count
- Meet the Hurly stage II: Total SCAR and Fistula counts > 0 at either screening or Day 1.
- Have Baseline AN count ≥ 3
- Have Baseline draining fistula count ≤ 20
- Do not take the following exclusionary medications during the exclusionary screening period or during Period 1:
- Any concomitant antibiotics for the treatment of HS (except the protocol allowed rescue medication which will result in counting the subjects as non-responders, or having the last observation prior to the use of these treatments carried forward).
- Anti-TNF-a (Humira), Methotrexate (MTX), cyclosporin, corticosteroids, and retinoids for any reason, or other medication for treatment of their HS that will confound the efficacy evaluation (to be determined and documented in the classification results prior to blind break).

Per-Protocol Population in Period 2 (PP2) will be defined separately.

Subjects included in the Per-Protocol Population will be analyzed as treated. That is, if a subject receives the treatment that is not the randomized assignment during their entire participation of a period, the subject will be analyzed according to the treatment that the subject actually received in the period.

Safety Population

The Safety Population will include all subjects who are randomized and have received at least one dose of study drug, excluding those subjects who are from study Site 138. Due to the reasons stated above safety data of subjects from site 138, including adverse events, will be listed separately only and not be included in the summary tables:

- The Safety Population in Period 1 (Safety1) is defined as all subjects who are randomized at baseline and have received at least one dose of study drug during Period 1.
- The Safety Population in Period 2 (Safety2) is defined as all subjects who
 received at least one dose of avacopan during Period 2.
- The All Avacopan Treated Population is defined as all subjects who receive at least one dose of avacopan in any treatment period.

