2) Non-Responder Imputation for Any Add-on Antibiotics/Other Concomitant Medications Use

All subjects with any add-on antibiotics (any antibiotics other than the concomitant at Baseline) or with dose increase from baseline concomitant antibiotics prior to Week 12, regardless the reason for use; or other concomitant medications listed below will be imputed as non-responders:

- Add-on antibiotics
- Concomitant Anti-TNF-α treatment
- Concomitant other systemic treatment for HS. E.g., methotrexate, cyclosporine, retinoids, and fumaric acid esters, etc.

3) LOCF for HiSCR

Subgroup Analysis

Subgroup analyses will be performed for the primary efficacy endpoint in the ITT1 Population.

The subgroups are defined as follows:

- Randomization stratification variables
 - Hurley Stage (II, III)
 - Concomitant antibiotic therapy (Yes, No)
 - Anti-TNF-α treatment (Treatment naïve, Previous treatment)
- Sex (Male, Female)
- BMI category: Normal (< 25 kg/m²), Overweight (25 − < 30 kg/m²), obese (30 − < 40 kg/m²), Morbid obesity (≥ 40 kg/m²)
- Age at diagnosis of HS (< median, ≥ median)
- Age at study entry (<65 years vs. ≥ 65 years)
- Duration of HS (< median, ≥ median)
- Race (White vs. None-White)
- Baseline AN count (<5, 5-10, >10)
- Baseline inflammatory nodule count (< median, ≥ median)
- Baseline abscess count (< median, ≥ median)

- Baseline draining fistula count (< median, ≥ median)
- Baseline modified Sartorius score (< median, ≥ median)
- Previous systemic HS treatment (includes TNF inhibitor use but excludes antibiotic use)
- Geographic distribution (Northeastern Region, Southeastern Region, Western Region, Midwestern Region, and Southwestern Region)

These summaries will be based on imputed data (NRI for binary variables). If the sample becomes sparse in one of the subgroup strata, the subgroup variable will be collapsed or removed from the subgroup analysis.

Exploratory Analysis

The avacopan 10 mg vs. 30 mg groups will be tested for the primary efficacy endpoint if the primary efficacy endpoint tests of both avacopan 10 mg vs placebo and avacopan 30 mg groups vs placebo are statistically significant in the ITT1 Population.

E. Secondary and Other Efficacy Endpoints Analyses

The following missing data handling rules will apply:

Secondary/Other Efficacy Endpoints

- For binary efficacy variables, NRI imputation method will be used for missing data. For NRS30 in Period 1, multiple imputation method will be applied similarly as the primary endpoint.

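### The SAP's Period 1 per-protocol rule excepts only rescue antibiotics, so as written it drops compliant subjects on permitted baseline doxycycline or minocycline; its corticosteroid item is also ambiguous

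*SAP*

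**What the plan says.** **The PP1 rule (SAP VI.J).** The lead-in describes the per-protocol set as ITT1 subjects who "do not have protocol deviations that could significantly affect the interpretation of the results for the primary endpoints". PP1 subjects must then satisfy every item on a list. One item is that they took none of the named exclusionary medications in the exclusionary screening period or Period 1. The first medication entry is "Any concomitant antibiotics for the treatment of HS (except the protocol allowed rescue medication which will result in counting the subjects as non-responders", and it continues with a last-observation rule for the same rescue users. The second entry begins "Anti-TNF-a (Humira), Methotrexate (MTX), cyclosporin, corticosteroids, and retinoids for any reason". SAP Section X repeats both.

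**What is permitted.**
- Protocol 4.2, criterion 6, excludes systemic antibiotics in general but excepts "subjects on systemic antibiotic treatment with doxycycline or minocycline who have been on a stable dose for at least 28 days" before Day 1.
- Protocol 3.1 makes concomitant antibiotic use a stratification factor: "Not more than 20% of subjects will be in stratum 2a as described above".
- Protocol 5.7 lets subjects stratified for antibiotic use stay on these drugs without a dose increase, and adds that "Investigators will be allowed to reduce the dose(s) or discontinue these ongoing antibiotic treatments during the study".
- SAP IV.A restates the permission: "Stable antibiotic therapy with doxycycline or minocycline is allowed as specified in the protocol".
- Protocol 5.7 names intralesional triamcinolone as one of two allowed lesion interventions, with two interventions allowed in Period 1. Protocol 8.8.1 says protocol-specified interventions do not make a subject a non-responder.

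**Where PP1 is used.** SAP VIII.D analyses the primary endpoint in PP1 as well as ITT1. SAP VIII.E does the same for the secondary endpoints.

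**The concern.** A per-protocol set should contain the subjects who followed the protocol. The antibiotic bullet instead removes subjects for a treatment that the protocol allows and that the randomisation stratifies on. A subject who took a stable baseline antibiotic exactly as permitted is out, while one who needed rescue antibiotics stays in as a non-responder. A programmer following the list would empty the antibiotic-Yes stratum from the supportive analyses of the primary and secondary endpoints.

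The corticosteroid item raises a related but weaker question. No route is given, and the rescue exception is written only into the antibiotic entry. If the item covers permitted intralesional injections, PP1 would drop subjects because of a post-randomisation event that the protocol neither forbids nor treats as non-response.

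**Working it through.** **Step 1. Follow one compliant subject through the text.** Take a subject on stable doxycycline for more than 28 days before Day 1, randomised in the antibiotic-Yes stratum, who continues without a dose increase.

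| Source | Result for this subject |
|---|---|
| Protocol 4.2, criterion 6 | Eligible |
| Protocol 3.1 and 5.7 | Stratified; may continue, reduce or stop |
| SAP VI.J lead-in | No deviation, so no ground for exclusion |
| SAP VI.J antibiotic bullet | Took an antibiotic for HS that was not rescue, so excluded |
| SAP VIII.D, sensitivity analysis 2 | Not an add-on antibiotic, so not forced to non-response |

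Sensitivity analysis 2 defines add-on antibiotics as "any antibiotics other than the concomitant at Baseline" and also catches dose increases. The SAP therefore draws the needed distinction there and omits it in PP1.

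**Step 2. Check against the planned test.** The CMH test in SAP VIII.D stratifies on allowed antibiotic use, Yes versus No, and the same endpoint is analysed in PP1. Under the literal rule the Yes level is essentially empty in PP1 and the factor carries no information. The sparse-stratum rule would let the test run, but it does not explain why the factor is there.

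**Step 3. Reproduce the plan's power.** Inputs from Protocol 8.3: HiSCR 30% on placebo, 50% on avacopan, 130 per arm, two-sided alpha 0.05, stated power about 90%. With pooled variance under the null,

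power = Φ{[0.20 − 1.96 × √(2 × 0.40 × 0.60 / n)] / √[(0.30 × 0.70 + 0.50 × 0.50) / n]}.

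At n = 130: (0.20 − 1.96 × 0.06076) / 0.05949 = 1.36, so power is 91.3%. At n = 121 (130 less the assumed 7% attrition) it is 89.3%. Both agree with the stated figure.

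**Step 4. Size the loss.** At the cap, 0.20 × 390 = 78 subjects, and 78 / 3 = 26 per arm. The documents do not give the actual share, so a range is assumed. The half-width is 1.96 × √(0.46 / n).

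| Share on baseline antibiotic | n per arm | Power | 95% CI half-width |
|---|---|---|---|
| 0% | 130 | 91.3% | 11.7 points |
| 5% | 123.5 | 89.9% | – |
| 10% | 117 | 88.2% | 12.3 points |
| 20% (cap) | 104 | 84.3% | 13.0 points |

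Starting from 121 per arm, the cap leaves 121 × 0.80 = 96.8 per arm and 81.6% power. No other PP1 criterion and no Site 138 exclusion is taken into account.

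**Step 5. The corticosteroid item, both readings.** For the narrow reading, its neighbours in the list are systemic drugs, and SAP VIII.B collects lesion interventions on the AE and Concurrent Procedures CRFs. For the literal reading, the entry applies whatever the reason for use, names no route, and SAP VIII.C itself calls the permitted injection a corticosteroid injection. The text does not settle the matter. Usage rates are not given, so the effect cannot be sized.

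**The case against.** The strongest defence is that nobody meant this. The list is headed as exclusionary medications, and stable doxycycline or minocycline is the stated exception to the exclusion. The lead-in speaks of deviations that affect interpretation. Membership is to be settled and documented before lock and unblinding, which gives a blinded step at which the wording could be applied sensibly. One could also argue that PP1 is stricter than an absence of deviations by design, since it requires a post-baseline lesion assessment, and that removing background antibiotics from a supportive set is a defensible choice. Finally, SAP VIII.D already plans an ITT1 subgroup analysis by antibiotic use, so the effect in these subjects will be reported anyway.

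Part of this stands. The exclusion was probably unintended, the ITT1 subgroup limits the loss of information, and the plan promises no power for PP1. It does not rescue the text. The bullets themselves define which medications are exclusionary, subjects must meet every criterion, and the pre-lock review applies those same criteria. Restoring these subjects at that step would mean departing from the written rule. If dropping them were deliberate, the SAP would need to say so, because the lead-in and the stratified test both point the other way. On corticosteroids the objection is fair that the literal reading is uncertain. The claim is ambiguity only.

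**Conclusion.** The concern holds. As written, the antibiotic criterion excludes protocol-compliant subjects on permitted baseline doxycycline or minocycline. The loss is at most 78 of 390 subjects and may be much smaller, because 20% is a ceiling.

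The consequence is confined to the supportive per-protocol analyses. For the antibiotic stratum it costs precision and generalisability. It does not bias the comparison in the remaining strata, because the factor is fixed at baseline and randomisation was stratified on it. The ITT1 primary analysis and its alpha are unaffected. The power figures assume equal loss across arms and the plan's 30% and 50% response rates.

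The corticosteroid item is an ambiguity of unknown size. It needs a clarifying line because the literal reading would be a post-randomisation exclusion.

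**What to change.** Before unblinding, amend SAP VI.J and make the same edits in its copy in Section X:

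1. In the antibiotic bullet, add an exception for doxycycline or minocycline permitted at baseline (antibiotic stratum Yes) and then continued, reduced or discontinued without a dose increase, as Protocol 5.7 allows. This matches the baseline exemption in sensitivity analysis 2.
2. Reconcile the corticosteroid item with Protocol 5.7 and 8.8.1 by stating that protocol-allowed intralesional injections within the permitted number are not a PP1 exclusion.

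The cost is two lines of text, each entered in two places. No new data are needed and trial conduct does not change.
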